For effectiveness, intervention theory of change (mediation mechanisms), and cost-benefit evaluations, the child and teacher effectiveness outcomes will be assessed and evaluated across 3 time points- baseline (**T1**, before PD), immediately after the PD/PTD (**T2**, about 3-4 months after T1), and 12 months later (**T3**, about 18 months after T1). Data from **multiple sources** will be collected. For child effectiveness outcomes, the primary outcome is mental health (externalizing and internalizing problems), and the secondary outcome is behavioral and cognitive domains (see Table 2 for measures). Parent and child report data will be used. Parents of target students will be interviewed by trained research staff (using English or Luganda, lasting 30-45 minutes). Child assessment will be carried out in school by research staff (lasting about 20-30 mins). For teacher effectiveness outcomes, the primary teacher outcome is EBI practice, which will be based on objective observation by an independent observation team (primary data source) and teacher-report (secondary data source). The observation measure has been validated and published in our previous trial study (see [name] KY, [name] J, et al. Transportability of an Evidence-based Early Childhood Intervention in a Low-Income African Country: Results of a Cluster Randomized Controlled Implementation Study. *Prevention Science*. 2017;18:964-75). The secondary teacher outcome will be social process (i.e., teacher-student and teacher-family relationship), based on parent and child report. All primary outcomes and most secondary outcome measures have been used and validated in our previous Ugandan studies (see Table 2 for measures and reliability information from our Ugandan studies). Costs will be measured using an activity-based micro-costing approach in the intervention cluster (school), and in the extended implementation phase in all clusters from 6 through 12 months (n=36 clusters). Costs of the intervention will include all program costs incurred (for *PD/PDT* training, coaching, and materials/resources). Research costs will be excluded. Cost data collection will utilize existing standardized cost extraction forms and procedures that have been validated from Co-I [name]’s work in Uganda and LMICs. Prior to use, these tools will be tailored and customized. **Research staff for family and observation data collection will be masked** to intervention conditions. To ensure masking, we will have an independent assessment team (led by a separate research coordinator), and members will not participate in any intervention activities. We will also train implementation team on protocol to prevent releasing assigned condition information. Teacher-report data collection will not be masked. The tablet and team approach of data collection that we used in our previous studies will be applied.

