## 9 Statistical Considerations

**Data Analysis Plan for Aim 1.** Prior to any outcome analyses, we will generate summary statistics for all data, summarizing with means and standard deviations for continuous variables and frequencies for categorical variables. The distribution of study variables and missing data patterns will be inspected. To estimate effectiveness, we will apply intention-to-treat (ITT) analyses and first focus on between-subject comparisons of intervention vs. control (comparing *PD* to control, comparing *PDT* to control, and comparing *PD* to *PDT*). We will estimate the impact of *PD* on children and teachers post-intervention (T2, 4-5 months after T1) and at one-year follow up (T3, 18 months after T1, or 12 months after T2). **Figure 4** below describe the model to be tested under Aim 1. School and class nesting will be considered, and a multiple imputation strategy will be applied to account for missing data. Linear mixed effect models, using SAS PROC MIXED, will be applied to examine short and longer-term impacts. We will first examine the immediate impact by modeling post-intervention outcomes (T2) as a function of intervention, adjusting for T1 outcome measures. The model accounts for between-subject (within-school and -class) correlation by including school- and classroom-level (when appropriate) random intercepts. The outcomes will be modeled as:  $Y_{ij} = \beta_1 I_j + \beta_2 C + \beta_3 X_{ij} + \gamma_j + \gamma_k + \epsilon_{ijk}$ , where  $Y_{ij}$  is the outcome for the student  $i$  in school  $j$ .  $I_j$  is intervention status (a categorical variable, with 3 levels) for school  $j$ , representing two dummy variables (control as the reference).  $C$  is the cohort indicator for

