school, where  $C=1$  if is in the second cohort, 0 for the 1st cohort.  $X_{ij}$  is the baseline value of the outcome for student  $i$  in school  $j$ . In the models,  $\beta_1$  represents the intervention impact,  $\beta_2$  is the effect of the second cohort,  $\beta_3$  is the effect of baseline measure,  $\gamma_j$  is the school-level random effect and  $\gamma_k$  is the class-level random effect (when appropriate), and  $\epsilon_{ijk}$  is the error term for student  $i$  in school  $j$  and  $k$  class. Next, we will study longer-term effectiveness outcomes (T2 to T3) by applying growth curve models and using repeated assessments over time. In these growth models, we will add time-relevant parameters to the model above, including school-level random slopes. The post-baseline scores will be modeled as a linear function of time/slopes, intervention indicator, and intervention-by-time interactions, adjusting for T1 scores and cohort. The long-term outcome will be modeled as:  $Y_{ij} = \beta_1 I_j + \beta_2 t + \beta_3 I_j * t + \beta_4 C + \beta_5 X_{ij} + \gamma_j + \gamma_k + \epsilon_{ijk}$ . A significant  $\beta_3$  would indicate the effect of the intervention depends on time; in this case, we will estimate the slopes for each condition, and the difference between the conditions with respect to the mean outcome scores. The analytical methods that we propose have been applied successfully in our previous US and LMIC studies. Cost-effectiveness analysis of *PD* and *PDT* implementation models will be examined using approaches that have been applied in previous school-based and parenting-based child mental health promotion research. The analysis will center on incremental cost-effectiveness ratios (ICERs), where the numerator represents the cost difference between the intervention arms and the control, and the denominator represents the difference in average intervention effects. To that end, the cost-effectiveness analysis of the intervention will involve examining how much the *PD/PDT* intervention costs to achieve a unit of effect relative to the control group. The effects of the intervention will be estimated using the effect sizes  $d$  (standardized mean difference between comparison groups) from an ITT approach. For the effectiveness outcomes, we will use an effect size of 0.2-0.4 as a benchmark; this corresponds to a small to medium effect size according to Cohen. We will calculate the ICERs and compute the per-participant cost per 0.2-0.4 SD change for each effectiveness outcome. Reporting of the analysis will follow the Consolidated Health Economic Evaluation Reporting Standards (CHEERS).

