**Figure 4. Aim 1 Effectiveness and Cost-Effectiveness Mechanisms**

**Data Analysis Plan for Aims 2.** For testing *PD/PDT* theory of change, Preacher's Multilevel Structural Equation Modeling (SEM) and MacKinnon's mediation model testing principles/strategies will be applied. Figure 5 below describes the model to be tested under Aim 2. Mediators (primary and secondary) will be examined separately. Only intermediate outcomes that show significant improvement will be examined in the mediation model testing. The mediation model will build on the effectiveness evaluation model (Aim 1 model), by including changing scores of mediators (T2-T1) and T2 to T3 child outcome trajectory because a mediation model is ideally tested in a design demonstrating time precedence in which the intervention occurs before the outcome. The mediation mechanism will be modeled as:  $Y_{ij} = \beta_1 I_j + \beta_2 t + \beta_3 I_j * t + \beta_4 M_j + \beta_5 C + \beta_6 X_{ij} + \gamma_j + \gamma_k + \epsilon_{ijk}$ .  $M_j$  is the value of the mediator at T2 and/or T3 for school  $j$ .  $\gamma_j$  and  $\gamma_k$  are the school- and class-level random effects. We will compare  $\beta_1$  and  $\beta_3$  from this model with the  $\beta_1$  and  $\beta_3$  from the effectiveness models that are not included the moderator ( $Y_{ij} = \beta_1 I_j + \beta_2 t + \beta_3 I_j * t + \beta_4 C + \beta_5 X_{ij} + \gamma_j + \gamma_k + \epsilon_{ijk}$ ). A significant effect of  $\beta_1$  and  $\beta_3$  in the mediation model will suggest a mediation effect. A conventional

[figure not shown]
Sober test described by Baron and Kenny will be applied next to test the significance of the mediation model. This modeling approach has been applied in our previous work. To confirm the model, Multilevel SEM will also be conducted (using Mplus).

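### The Aim 2 plan defines the mediator in two conflicting ways, and the one in the equation allows a T3 value that breaks the plan's own time order and could bias the indirect effect

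*Combined protocol and SAP*

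**What the plan says.** All of this is in section 9 of the combined protocol and SAP unless noted.

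- **Mediator in the text (Data Analysis Plan for Aims 2).** The model extends the Aim 1 model "by including changing scores of mediators (T2-T1) and T2 to T3 child outcome trajectory". The reason given is that "a mediation model is ideally tested in a design demonstrating time precedence in which the intervention occurs before the outcome".
- **Mediator in the equation (same paragraph).** The term M_j "is the value of the mediator at T2 and/or T3 for school" j. The equation has a child baseline term but no T1 mediator term.
- **Child outcome (Aim 1 longitudinal model, which Aim 2 extends).** "The post-baseline scores will be modeled as a linear function of time/slopes, intervention indicator, and intervention-by-time interactions, adjusting for T1 scores and cohort". The outcome rows are therefore T2 and T3.
- **Timing.** Section 6.1 says that "the child and teacher effectiveness outcomes will be assessed and evaluated across 3 time points- baseline", immediately after the intervention, and follow-up. Section 9 places the last of these "at one-year follow up (T3, 18 months after T1, or 12 months after T2").
- **Entry to mediation testing.** "Only intermediate outcomes that show significant improvement will be examined in the mediation model testing". No time point is named.
- **Test.** Intervention coefficients are compared between models with and without the mediator. Then a "test described by Baron and Kenny will be applied next to test the significance of the mediation model". The name is printed as Sober; I read it as Sobel. A multilevel SEM follows as confirmation, with no mediator timing stated.

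**The concern.** The two definitions differ in timing (T2 against T2 and/or T3) and in form (change score against raw value). An analyst following the equation may use T2, T3 or both, and the choice can be made after the data are seen.

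The T3 option matters because T3 is the last assessment in the effectiveness evaluation. The later T4 in the section 6.1 timeline covers control schools only, after they have received T-Wellness. No three-arm child outcome comes after a T3 mediator.

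The rival explanation is that child behaviour changes the teacher. Section 1.1 makes this plausible: it lists pupil misbehaviour among the sources of teaching stress, and says that stressed teachers may be less able to apply the strategies over time. Stress management and strategy use are the two hypothesised mediators. A reverse path of this kind, combined with a T3 mediator, could produce an apparent indirect effect where teacher practice does nothing for children. The plan has no reverse-path check and does not restrict T3 mediators to a sensitivity analysis.

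**Working it through.** The documents give no power, ICC or effect figure for Aim 2, so there is no stated number to reproduce. The check is of time order, then of the consequence under stated assumptions.

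**Time order**

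| Mediator | Against child T2 score | Against child T3 score |
|---|---|---|
| T2-T1 change, or T2 value | same wave | earlier |
| T3 value | later | same wave |

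The T3 value precedes neither outcome. The T2-based mediator precedes one of the two. The T2-to-T3 interval is 12 months in sections 6.1 and 9 but 6-7 months in the note to the section 6.1 timeline. T3 follows T2 in both, so the table stands.

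**Size of the bias with no true mediation**

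From the documents: 12 schools per arm. Assumed, on standardised school-level scores: intervention to T2 mediator 0.8; intervention to T2 child score 0.5; T2 to T3 stability 0.6 for mediator and child score; residual SD 1 at T2 and 0.8 at T3; reverse path c from the T2 child score to the T3 mediator; no path from mediator to child. The outcome is the mean of the T2 and T3 child scores.

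- Total effect = 0.5 × (1 + 0.6)/2 = 0.40
- Intervention to T3 mediator: a = 0.6 × 0.8 + 0.5c = 0.48 + 0.5c
- Variance of the T3 mediator within arm = 0.36 + c² + 0.64 = 1 + c²
- Mediator coefficient: b = 0.8c / (1 + c²)
- Apparent share mediated = ab / 0.40; apparent direct effect = 0.40 - ab

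| c | a | b | ab | share | direct effect (from 0.40) | b significant at 5% | Sobel significant |
|---|---|---|---|---|---|---|---|
| 0.2 | 0.58 | 0.154 | 0.089 | 22% | 0.31 | 13% | 1.1% |
| 0.3 | 0.63 | 0.220 | 0.139 | 35% | 0.26 | 22% | 1.8% |
| 0.4 | 0.68 | 0.276 | 0.188 | 47% | 0.21 | 34% | 3.6% |

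The last two columns are simulated (2,000 to 3,000 trials per row). The simulated share was 23 to 47%. With a T2 mediator the share is about 0 and b is significant in about 5% of trials.

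**Second simulation**

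This one used school means of 55 children, a child effect of 0.3 (the middle of the 0.2-0.4 benchmark in section 9), T1 adjustment, an assumed ICC of 0.05 or 0.10, and an assumed teacher effect of 0.8 school SD. Results for the T3 mediator:

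| Reverse path | Share | Sobel significant |
|---|---|---|
| 0 | about 0% | 0.4-0.8% |
| 0.3 | 20-25% | 6-7% |
| 0.5 | 43-49% | 28-32% |
| 0.7 | 78-88% | 72-78% |

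With the T2-T1 change, Sobel rejection stayed below 1% and the share within 1% of zero at every setting. If the intervention had no direct effect on teachers (ICC 0.10), T3 rejection fell to 0.3%, 3.4% and 19.1% at paths of 0.3, 0.5 and 0.7.

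**Two limits on the T2 repair**

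- *Same-wave feedback.* Neither simulation above lets the T2 child score affect the T2 mediator. If it does, with a path of 0.2 to 0.4, the T2 mediator coefficient on the pooled outcome is significant in 13 to 35% of trials.
- *Adjusting for the T2 child score.* Modelling the T3 child score given the T2 child score removes that problem but changes the question. Suppose true mediation acts wholly by T2, with mediator-to-child path m. The true indirect effect on the pooled outcome is 0.8 × m × 0.8 = 0.64m: 0.26 at m = 0.4 and 0.38 at m = 0.6. The adjusted model estimates about 0, with about 5% coefficient rejection, against 36 to 66% for the T2 mediator on the pooled outcome.

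**The case against.** The strongest reply is that the plan does not commit to T3. It states a correctly motivated T2-T1 definition first, with its reason, and T3 enters through one loose phrase. Figure 5, which describes the Aim 2 model, is not visible in the text reviewed and may fix the timing. This stands: the defect is an unresolved contradiction that leaves a biased option open. A reader might infer that a reverse effect would be reported as mediation. The documents support only that it could be.

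A second reply concerns the 13 to 34% rejection rates for the mediator coefficient, which a reader might take as the false-positive rate for mediation. The plan does not declare mediation on that coefficient. Its named test rejects in 1.1 to 3.6% of the same trials, below the nominal 5%. This also stands. The bias in the point estimate remains, as does the shift in the intervention coefficient, and the plan draws on both.

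Third, a T2 mediator is not clean either, because it shares a wave with the T2 child score. That is correct. It supports adding a sensitivity analysis; it does not make the T3 option acceptable. Nor does it justify making the T2-adjusted model primary, since that model misses any mediation complete by T2, and section 9 plans to estimate the immediate T2 impact first.

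**Conclusion.** The contradiction is certain from the text, and so is the break in time order if a T3 mediator is used. How much harm follows depends on a reverse path that the documents make plausible but do not quantify. At assumed paths of 0.2 to 0.4, roughly a quarter to a half of the total effect could wrongly appear mediated, with few significant Sobel results. In the second simulation, paths of 0.5 to 0.7 gave frequent false rejections (28 to 78%) when the intervention also affects teachers directly. These figures illustrate and are not forecasts.

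The documents do not show that Aim 2 would be wrongly declared supported, or that T3 alone is the source of the timing problem. The point concerns Aim 2, including any mediation model carried forward into Aim 3. The Aim 1 effectiveness estimates do not depend on it. It should be corrected before analysis.

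**What to change.** 1. In the Aim 2 equation, replace the T2 and/or T3 wording with the definition already in the text: M_j is the T2-T1 change in the mediator for school j. An equivalent choice is the T2 value with the T1 mediator value added as a covariate. Name one of these in advance, and state that the multilevel SEM and the entry rule for mediators use the same T2 timing.
2. Use T3 mediator values only to describe whether teacher practice is sustained, not for any claim of mediation.
3. Add a sensitivity analysis: the T3 child score on the T2-based mediator, adjusted for the T1 and T2 child scores. State that it captures only mediation arising after T2, so a null result there does not refute earlier mediation.
4. If Figure 5 shows mediator timing, bring it into line.

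All the scores are already scheduled. The cost is a wording change, a little more analysis, and no T3-mediator result for mediation.

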**Figure 5. Aim 2 PD and PDT Mediation Mechanisms**

**Data Analysis Plan for Aims 3.** For moderation model testing, we will apply similar approaches as in Aim 1 and add the moderator and moderator-by-intervention interaction terms in the analysis. Figure 6 below describes the model to be tested under Aim 3. For models with a significant moderator-by-intervention term on teacher effectiveness outcomes, we will then further test mediation-moderation mechanisms by expending the mediation model described above. These methods have been utilized in our previous studies.

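### Aim 2 reads significant direct effects as a sign of mediation: the sentence is wrong as written, and the mediator it relies on is defined in two ways

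*Combined protocol and SAP*

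**What the plan says.** The Data Analysis Plan for Aims 2 (Section 9) names multilevel SEM and MacKinnon's mediation principles as its methods. It then writes the outcome model with β1 for intervention, β3 for intervention by time and β4 for the mediator M_j in one equation. In order, it says:

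- Entry condition: "Only intermediate outcomes that show significant improvement will be examined in the mediation model testing".
- The model extends the Aim 1 model "by including changing scores of mediators (T2-T1) and T2 to T3 child outcome trajectory", and does so "because a mediation model is ideally tested in a design demonstrating time precedence in which the intervention occurs before the outcome". Under the equation, however, M_j "is the value of the mediator at T2 and/or T3 for school" j.
- β1 and β3 are compared with those "from the effectiveness models that are not included the moderator". The last word evidently stands for mediator.
- A significant β1 and β3 "in the mediation model will suggest a mediation effect".
- A Sobel test (misspelled in the text) "will be applied next to test the significance of the mediation model", and a multilevel SEM in Mplus is run as confirmation.

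The Data Analysis Plan for Aims 3 adds that, after a significant moderator-by-intervention term on a teacher outcome, "we will then further test mediation-moderation mechanisms by expending the mediation model described above". The Aim 2 hypothesis in Section 2 is an indirect path from intervention through teacher behaviour to child outcome. Nothing in the text redefines β1 or β3 as indirect effects. Figure 5 is not reproduced in the text available, so it could not be checked.

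**The concern.** With M_j in the equation, β1 and β3 measure what the intervention does apart from the mediator. The sentence takes that remainder as a sign of mediation, which is the wrong way round. An analyst who applied it literally could report mediation on the strength of a direct effect, or dismiss a mediator that carries the whole effect. The paragraph does not say what happens if this reading disagrees with the Sobel test or the SEM.

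The two definitions of M_j add a second problem. They decide whether the planned comparison of β3 between models can show anything, and whether the mediator is measured before the outcome it is meant to explain.

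**Working it through.** The plan gives no numerical target for the mediation test, so there is no figure to reproduce. The check is algebra, followed by simulation for size.

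**Step 1. What the coefficient means.** Let M = a·I + e₁ and Y = c′·I + b·M + e₂. Substituting, Y = (c′ + a·b)·I + error, so total = direct + a × b. Example with assumed values a = 1.5 and b = −0.2 (or b = 0):

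| Situation | Total effect | Coefficient of I with M in the model | a × b |
|---|---|---|---|
| Full mediation | 1.5 × (−0.2) = −0.30 | 0 | −0.30 |
| No mediation (b = 0) | −0.30 | −0.30 | 0 |
| Partial mediation | −0.30 − 0.30 = −0.60 | −0.30 | −0.30 |

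The third column is the same with no mediation and with partial mediation, so its significance cannot tell them apart. Simulation (36 schools, 55 children each, 5,000 runs, assumed child ICC 0.02–0.10, two-sided 5%) agrees. In the order of the table, β1 was significant in about 5%, 42–92% and 43–93% of runs, and the Sobel test in 74–95%, 2–3% and 75–94%. These β1 rates illustrate the algebra. They are not the plan's criterion, which names β1 and β3 together.

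**Step 2. The criterion as printed (β1 and β3 both significant).**

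- From the documents: 36 schools, 12 per arm, about 55 families and 15 teachers per school, two cohorts (Protocol Summary; Section 6.1 timeline). Child effect 0.39 and teacher effect 0.55–1.03 come from the Uganda results in the Section 1.1 evidence table; 0.20 is the lower benchmark in the Aim 1 plan.
- Assumed (base; range): child ICC 0.05 (0.02–0.10), teacher ICC 0.15 (0.05–0.30), teacher effect 0.8 (0.55–1.03), child effect 0.39 (0.20 or 0.39).
- Assumed and not varied: T2–T3 correlation 0.8 for schools and 0.5 for children, and no variance reduction from baseline.
- Method: PD versus control, school-mean analysis, 20,000 base runs, and 4,000 runs in each of 54 settings. Rates are conditional on a significant effect on the mediator, as the plan requires (98.7% of base runs; 58–100% over settings).

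| Intervention effect on T2–T3 slope | No mediation | Full mediation | Settings where the no-mediation rate is higher |
|---|---|---|---|
| None | 4.1% (0.8–5.7%) | 0.5% (0.2–0.8%) | 54 of 54 |
| 0.1 SD | 16.1% (1.6–31.7%) | 2.1% (1.1–5.1%) | 52 of 54 |

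The slope effect is direct under no mediation and runs through M under full mediation. A rough check of the first row treats the two tests as independent. β1 was significant in 84% of base runs with no mediation and in 6% with full mediation, and β3 is significant 5% of the time by chance. So 0.84 × 0.05 = 4.2% and 0.06 × 0.05 = 0.3%. Repeat base runs gave 3.9–4.5% and 0.5–0.6%.

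**Step 3. What the β3 comparison can show.** With t = 0 at T2 and t = 1 at T3, subtract the two equations for a child.

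- If M_j is one value per school, as a T2–T1 change is, it cancels: Y(T3) − Y(T2) = β2 + β3·I + error. Adding M_j leaves β3 where it was. With a 0.10 slope effect wholly mediated by such an M, β3 was 0.095 without M, 0.095 with M, and 0.002 once an M × t term was added. With 30% of T3 missing, adding M alone moved β3 by at most 0.003.
- If M takes its T2 and T3 values, β4·[M(T3) − M(T2)] remains and β3 can fall. When the intervention effect on M grew by 0.2 or 0.4 SD, β3 fell from 0.106 to 0.012 and from 0.181 to 0.003 without an M × t term. But M at T3 is then concurrent with the T3 child outcome.

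**The case against.** The best defence is that the sentence decides nothing. Its verb is only to suggest. Multilevel SEM is named at the head of the Aim 2 plan, the Sobel test follows without any condition on β1 or β3, and the SEM confirms. Coming straight after a with-and-without comparison, in a paragraph with two other slips of wording, the sentence may have been meant to say a significant reduction in the coefficients. All of this stands as to reach. It does not rescue the wording, because the plan never says that a reduction was meant.

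A reader might infer three stronger things that the documents do not support.

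- **That β1 and β3 must be significant before the Sobel test is run.** The Sobel test comes next in order, but the only written screen is on the intervention effect on the mediator.
- **That mediation would often be declared falsely.** High rates belong to β1 alone. With no slope effect the printed criterion is met in 4.1% of runs without mediation, so there the practical fault is that it hardly ever fires. The 16.1% needs an assumed direct slope effect.
- **That a T3 mediator breaks the plan's own timing rule.** The precedence the plan writes is intervention before outcome, which a T3 mediator respects. Mediator before outcome is a sound standard but not the one stated. The two definitions still have to be reconciled.

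The reach into Aim 3 is also conditional: that plan extends the mediation model, not this sentence, and only after a significant moderator term.

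**Conclusion.** The sentence is wrong as written and should be corrected before analysis. Significance of β1 and β3 with the mediator in the model concerns the direct effect. Under full mediation the direct effects are zero: β1 tends to zero, and so does β3 where the model lets the mediator act on the slope. With an irrelevant mediator both keep the whole effect. This rests on algebra and on the printed equation. The simulated rates rest on assumed ICCs, effects and correlations and only indicate size.

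Harm is confined to Aim 2, and to Aim 3 where it extends this model, and arises only if the sentence is used to decide or screen. If the Sobel test or the SEM decides, inference is unaffected. Separately, M_j needs one definition. With the time-constant one and no M × t term, an unchanged β3 says nothing about mediation of the slope.

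**What to change.** Replace the sentence with:

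> With the mediator in the model, β1 and β3 are direct effects; their attenuation relative to the model without the mediator is descriptive. Mediation is judged by the indirect effect a × b (the planned Sobel test and multilevel SEM), whether or not β1 or β3 is significant.

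Then:

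- Use the already stated T2–T1 change as M in the main mediation analysis, and label any analysis with a T3 mediator supplementary.
- Either add an M × t term, stating in advance whether a × b refers to the T2 level or the T2–T3 slope, or do not compare β3 between models.
- Correct moderator to mediator in the comparison sentence.

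The order of Sobel test and SEM, the interval method and the contrasts are for the investigators to choose. No multilevel SEM was fitted here, so this check cannot vouch for any interval with 36 schools. In school-mean runs with maximum-likelihood standard errors, a Monte Carlo interval gave about 8% false positives.

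The cost is wording and at most one extra model term. The tests and the T2–T3 trajectory are already planned, and no new data are needed.

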Population	The study populations include: (1) Teachers for the T-Wellness User-centered & Optimization testing (n=60; from 4 non-RCT schools in year 1); (2) Intervention implementers (n=8; 6 TTC trainers and 2 mental health professionals from urban/Kampala and rural/Hoima regions; (3) Primary school teachers/head teachers (n=540) from 36 schools and PTA leaders (n=24) from 24 intervention schools; and (4) Children and caregivers (n= 1980 parent-child pairs) from 36 study schools.
Study Sites	36 schools (12 receiving PD, 12 receive PDT, and 12 control).
Number of participants	2544 adults and 1980 children for Aims 1-3 (This is not including 60 teachers for the T-Wellness User-centered testing during Year 1 preparation year).

[figure not shown]

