## 6 Study Procedures and Schedule

### 6.1 Study Procedures/Evaluations/Procedures/Timeline

The three effectiveness and mechanism testing aims (Aim 1-3) will be accomplished by applying a matched-pair cRCT and hybrid effectiveness-implementation design. A mixed methods design with qualitative and quantitative data collection will be applied. The school will be the unit of randomization because the program is applied at the school-level and builds a “school community” of teachers who promote students’ mental health. The three-arm cRCT design allows us to simultaneously test *PD* effectiveness and study the added value of a package (T-Wellness) to address a critical practical task-shifting challenge (teacher stress). In addition, the Hybrid design that considers CFIR domains of implementation contexts (in Figure 1) allows us to rigorously study other EBI effectiveness-implementation mechanisms, which can further inform decisions about optimal deployment and generalized impact, and may accelerate the introduction of other valuable innovations into practice. Study tasks and timeline are listed in Table 1 below.

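### The only significance test named for Aim 2 mediation is the Sobel test, which is conservative for modest paths with 12 schools per arm; a Monte Carlo interval with t draws is a better choice

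*Combined protocol and SAP*

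**What the plan says.** The Aim 2 analysis plan in Section 9 has these elements.

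- **Framework:** multilevel SEM and "MacKinnon's mediation model testing principles/strategies", with no particular test or interval chosen.
- **Entry rule:** "Only intermediate outcomes that show significant improvement will be examined in the mediation model testing".
- **Mediator:** the term in the outcome model "is the value of the mediator at T2 and/or T3 for school" j. It varies between schools, not between children.
- **First criterion:** a significant effect of the intervention coefficients β1 and β3 "in the mediation model will suggest a mediation effect".
- **Significance test:** a conventional Sobel test (printed as Sober), attributed to Baron and Kenny, "will be applied next to test the significance of the mediation model".
- **Confirmation:** multilevel SEM in Mplus, with no statement of how the indirect effect will be tested there.

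Section 6.1 says: "The school will be the unit of randomization because the program is applied at the school-level". The Protocol Summary gives 36 schools, 12 per arm. No Monte Carlo, product-distribution or bootstrap interval for the indirect effect appears in the document.

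**The concern.** The indirect effect is a product: the intervention effect on the mediator (a) times the mediator effect on the child outcome (b). With a school-level mediator, both are estimated from 24 schools in a two-arm contrast, or at most 36. Sobel divides the product by a delta-method standard error and refers the ratio to a normal distribution. Unless at least one path is strong, the product is skewed and peaked. The test then rejects too rarely when there is no mediation, and misses true mediation too often.

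Mediation is the whole of Aim 2, and Aim 3 extends the same model. The number of schools is fixed, so the choice of test is one of the few ways left to gain power.

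**Working it through.** The plan states no power, alpha or indirect-effect size for Aim 2, so there is no figure to reproduce.

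**Inputs from the documents.** There are 12 schools per arm, about 15 teachers and about 55 children per school (Protocol Summary). Prior effects are in the ParentCorps evidence table of Section 1.1: teacher practice d = 0.55-1.03 (Uganda) and 0.32-0.69 (Nepal); child mental health d = 0.39-1.08 (Uganda) and 0.20-0.47 (Nepal).

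**Assumptions.** ICC 0.10 for teachers and 0.05 for children, full mediation, two-sided alpha 0.05, analysis of school means.

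**Step 1, algebra.** Sobel z = za·zb / √(za² + zb²). If both paths just reach 1.96, Sobel z = 1.96/√2 = 1.39. With equal z on both paths, each must reach 1.96 × √2 = 2.77.

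**Step 2, the plan's scale.** Variance of a school-mean mediator = 0.10 + 0.90/15 = 0.16 (SD 0.40). With 12 schools per arm, SE(a) = √(0.16 × 2/12) = 0.163. For Sobel to reach 1.96, zb must be at least 1/√(1/1.96² − 1/za²):

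| Teacher effect (SD) | za | zb needed |
|---|---|---|
| 0.40 | 2.45 | 3.27 |
| 0.55 | 3.37 | 2.41 |
| 0.70 | 4.29 | 2.20 |
| 1.03 | 6.31 | 2.06 |

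The penalty is heavy at 0.40 SD and nearly gone at 1.03 SD.

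**Step 3, type I error with b = 0, by simulation.** Two arms of 12 schools, unit residual SD, a in school-mean SDs (a = 1.0 is a teacher effect of 0.40 SD here). There were 4,000 runs, or 2,000 for the bootstraps, which resampled schools within arm.

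| Method | a = 1.0 | a = 2.0 |
|---|---|---|
| Sobel | 1.5% | 3.8% |
| Monte Carlo, normal draws | 4.1% | 5.9% |
| Monte Carlo, t draws | 3.0% | 4.6% |
| Percentile school bootstrap | 5.9% | 8.0% |
| Bias-corrected school bootstrap | 8.6% | 10.2% |

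On the plan's scale, at teacher effects of 0.40-0.70 SD, Sobel type I error was 1.5-3.7% and the t-draw interval 2.7-4.9%. Normal draws reached about 7%.

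**Step 4, power at a child effect of 0.20 SD, 24 schools.** Here b = 0.20/a. Variance of a child school mean = 0.05 + 0.95/55 = 0.067, taken as the total within-arm variance:

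| Teacher effect (SD) | Sobel | Monte Carlo, t draws |
|---|---|---|
| 0.40 | 64% | 65% |
| 0.55 | 62% | 71% |
| 0.70 | 51% | 57% |

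If 0.067 is instead the residual variance after the mediator, the t-draw gains are about 6-10 points. Across repeated runs the range is about 2-11 points with 24 schools. With 36 schools in two equal arms it is about 1-6.

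**Step 5, the entry rule.** Requiring a significant mediator effect first leaves gains of about 1, 8.5 and 6 points in the three rows above.

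**Step 6, large effects.** At a child effect of 0.39 SD or a teacher effect of 1.03 SD, the gain is about −0.5 to +2 points.

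**The case against.** A reader might infer more than the documents support, in four ways.

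- **That Aim 2 rests on Sobel alone.** It does not: the plan also has the β1/β3 criterion, the MacKinnon citation and the confirmatory SEM. But a significant intervention coefficient with the mediator in the model is not a test of a×b, the citation selects no method, and the SEM step names no inference for the product. Sobel remains the only named significance test.
- **That any resampling interval is a free improvement.** The school bootstrap is not: with 12 schools per arm, part of its apparent power is excess type I error. Normal-draw Monte Carlo intervals are also somewhat liberal, so their larger gains should not be quoted as the benefit.
- **That Sobel is always conservative here.** At a teacher effect of 1.03 SD, the top of the Uganda range, its type I error was 5.4% with 24 schools.
- **That 0.20 SD is the plan's own Aim 2 effect.** The 0.2-0.4 range in Section 9 is a benchmark for cost-effectiveness ratios. The earlier Uganda trial reported child effects from 0.39 up, where the choice of test hardly matters. The value 0.20 is the lower end of the Nepal range, which comes from a pre-post comparison.

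It is also fair that one three-arm model lets all 36 schools inform the b path, so 24 schools is the less favourable case. These points limit the size of the gain and the choice of remedy. They do not supply a better test in the plan.

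**Conclusion.** The concern holds in a limited form. Sobel is a poor choice as the one named test of a school-level indirect effect with 12 schools per arm, because it is conservative when the paths are modest. A t-draw Monte Carlo interval is closer to nominal size there and more powerful. It makes little difference when either effect is large.

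The sizes are illustrative. They rest on assumed ICCs and full mediation, and on school means without class effects, growth slope, cohort term or multiple imputation. The 36-school runs used two equal arms, not the plan's three-arm fit. The direction for modest paths follows from the algebra and does not depend on the assumed ICCs. The misprinted test name is not part of the finding.

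**What to change.** In the Aim 2 plan of Section 9, replace the Sobel sentence with one to this effect: mediation will be tested with a two-sided 95% Monte Carlo interval for the school-level indirect effect, drawing each path from a t distribution centred on its estimate, scaled by its standard error, with school-based degrees of freedom; mediation is declared when the interval excludes zero.

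In a two-arm contrast of n schools, the check used n − 2 degrees of freedom for a and n − 3 for b (22 and 21 with 24 schools). Further school-level covariates such as cohort would reduce these. Any school bootstrap should be labelled a sensitivity analysis.

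The cost is one SAP sentence and slightly more analysis work. No new data or schools are needed.
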